The primary objective of this study is to determine whether implementing the Pathway Platform in primary care improves adherence to measurement-based care practices.

Secondary objectives include determining whether implementing the Pathway Platform improves additional clinical process measures and depression response and remission outcomes.

Design and Outcomes

A pre- and post- study design is utilized to assess the impact of implementing the Pathway Platform in the primary care setting. Up to 20 primary care sites will be identified to participate in the study. Care team members involved in depression management will receive education on evidence-based clinical practices for depression care, such as measurement-based care practices and shared-decision making. Clinics with behavioral resources will also receive additional education on behavioral health integration. Training on how to onboard patients to use the Pathway Platform and utilize electronic medical records to view data collected in the Pathway Platform will also be provided. Study outcomes identified in this protocol will be assessed among 200 patients who will be enrolled in the Pathway Platform (post-implementation cohort). Outcomes will also be assessed in another 200 patients from the same participating clinics prior to study implementation (pre-implementation cohort). Implementation success will be evaluated by comparing study outcomes among the two cohorts with a total sample size of 400 patients (of which 200 will receive the intervention and 200 will not). The primary outcome is PHQ-9 utilization over six months and will be compared between the pre- and post- implementation cohorts. Additional process measures will be compared, including shared-decision making, medication adjustments, referrals to behavioral health, primary care follow-up post hospitalizations, and remission and response. Data collected in the Pathway Platform will also be evaluated to explore pre-defined patient outcomes. Additional outcomes will be explored in data captured from patients who continue to use the app beyond the initial 6 month study period.

Sample Size and Population

The study will take place in up to 20 primary care clinics within Advocate Aurora Health Care that are representative of different geographic locations, patient populations, and care models for

depression management, including behavioral health integration models.

The Pathway Platform consists of a mobile app for patients and a care team interface that can be accessed through Epic. We intend to enroll 200 patients who meet the eligibility criteria for this study and agree to download the Pathway Platform. An additional 200 patients will be identified from the same participating clinics to form the pre-implementation cohort. These are patients who visited the participating clinics at least 6 months prior to study implementation; they will not be actively enrolled into the study and their data will be collected retrospectively through chart reviews and electronic data pulls.

LIST OF ABBREVIATIONS

AE	Adverse Event
APA	American Psychiatric Association
APPS	Mobile Health Applications
ASEX	Arizona Sexual Experience Scale
CCM	Collaborative Care Model
DSST	Digit Symbol Substitution Test
ED	Emergency Department
EMR	Electronic Medical Record
GAD	Generalized Anxiety Disorder
GAS	Goal Attainment Scale
GAD	Generalized Anxiety Disorder
IRB	Institutional Review Board
IQR	Interquartile Range
MBC	Measurement Based Care
MDD	Major Depressive Disorder
PAM-13	Patient Activation Measure
PDQ-D5	Perceived Deficits Questionnaire- Depression
PHQ-2	Patient Health Questionnaire-2
PHQ-9	Patient Health Questionnaire Depression
PROMIS	Patient-Reported Outcomes Measurement Information System
PSD-6	PROMIS Sleep Disturbance 6a
PTSD	Post-Traumatic Stress Disorder
SAE	Serious Adverse Event
SD	Standard Deviation
SDM	Shared-Decision Making Model
SSR	Special Situation Report
WSAS	Work and Social Adjustment Scale
WHO-5	World Heart Organization- Five Well Being Index

1 STUDY OBJECTIVES

1.1 Primary Objective

The primary objective of this study is to determine whether implementing the Pathway Platform in primary care improves adherence to measurement-based care practices. We hypothesize improved clinical processes in measurement-based care, measured by PHQ-9 utilization among patients attending clinics post-implementation compared to those attending clinics pre-implementation.

1.2 Secondary Objectives

Secondary objectives include determining whether implementing the Pathway Platform improves additional clinical process measures and MDD response and remission outcomes. Patient outcomes and Pathway Platform utilization will be explored among patients using the Pathway Platform.

2. BACKGROUND AND RATIONALE

2.1 Background

Health-related technology solutions that utilize mobile phones, known as mobile health applications (apps), have the potential to expand health interventions beyond the traditional face-to-face patient visit. For the healthcare provider, mobile apps can offer low cost and easily scalable interventions to monitor and improve services to patient populations that are difficult to retain in treatment and may promote better health.¹ Uptake of health-related mobile apps has increased in recent years as technology barriers such as access, knowledge, and product usability have improved, reducing obstacles for ‘digitally excluded’ subpopulations (e.g., poor, rural, and older).² Consensus exists that the availability of a mobile app for depression management that is user friendly and aligns with busy office practice would likely be adopted by end users.³⁻⁴ Patients with depression and their treating provider may benefit from the use of a mobile health app to assist in disease management.

American Psychiatric Association (APA) clinical guidelines recommend measurement-based care (MBC) in treating depression, defined as a psychiatric evaluation including quantitative measures of symptoms, level of functioning, and quality of life. APA guidelines cite several studies that have shown benefits in using quantitative measures during an initial screening and also for monitoring depression throughout treatment.⁵ A mobile app may promote MBC by allowing patients to remotely answer quantitative instruments, such as the PHQ-9, which can be uploaded into their electronic medical records (EMR) for in office visits and physician monitoring.⁵ A study

by Torous et al. found that while in person paper scores and app scores were strongly correlated ($r=.84$), PHQ-9 app scores were consistently higher over a 30 days period.⁶ An overall conclusion of this study was that collecting PHQ-9's through a mobile app may be more sensitive than the traditional PHQ-9.⁶ Increased consultation times are often cited as a barrier to MBC implementation.^{5,7} An app may save time as the physician will only need to review PHQ-9 instead of administering the questions during the visit. Although the validity of the PHQ-9 has been shown in studies, further research is needed to assess its ability to track outcomes of depression therapy over time.⁷ This systematic approach to treatment may have positive effects on the patient-physician relationship and enhance shared decision making.⁵

A shared decision-making (SDM) model of interaction can foster patient provider engagement as well as increase patient satisfaction.⁸ Several studies have found that individuals suffering from a mental illness want a larger part in the treatment decision making process.⁹ A common barrier for SDM is a physician choosing a treatment plan that is not mutually agreed on by both the physician and patient. This can be overcome by increasing education and further clarifying the benefits of a specific treatment plan to align with the patient's values.⁹ Incorporating a SDM model may help increase adherence to drug treatment in a primary care setting.⁸ Mobile technology can enhance SDM.

A collaborative care model (CCM) that involves behavioral health integration within primary care is another evidence-based practice that enhances depression management. Collaborative care is a systematic approach that improves patient education and integrates mental health professionals or other care extenders, such as nurses, into the primary care clinic to help primary care physicians provide treatment in conformity with evidence-based guidelines.¹⁰ CCM's have been shown to improve outcomes of patients with major depression.¹¹

We hypothesize that integrating the Pathway Platform to support measurement- based care and shared decision- making, will improve the clinic workflow, depression management, adherence to medication, patient-provider engagement and improve depression outcomes and care.

2.2 Study Rationale

Major Depressive Disorder (MDD) is a serious public health concern worldwide with ample documentation demonstrating that it is one of the leading contributors to the global burden of disease and is currently the leading cause of disability worldwide.¹²⁻¹³ Moreover, the economic burden of MDD is estimated to total \$210.5 billion with approximately 50% of the cost being attributable to impairment in role function.¹³⁻¹⁵

A selection of mobile apps has been developed and are available for depression management.

However, many are patient facing only and have not implemented a care team interface. Most of these apps have been assessed for effectiveness in a research setting only and have not been integrated within clinic workflow resulting in lack of adoption by the care team and by healthcare systems.

This study builds on prior work that piloted a mobile App for feasibility and depression management, the *Pathway app*. The first iteration of the Pathway App included patient reported outcomes related to depression, wellbeing, cognitive symptom tracking, medication adherence and side effects. Pilot results confirmed the feasibility of using the Pathway app in patients with depression and showed a trend in patient engagement in the app arm, albeit in a small sample size. The Pathway pilot and feasibility study included qualitative assessments with patients and clinicians that highlight the need to enhance the flow of real time data shared with the care team and the need to integrate within the care team work flow including real time data sharing of the patient's app data within the EMR¹⁶. It also highlighted the need for care team education on measurement-based care, shared-decision making, and collaborative care and on how to utilize the Pathway App to improve these processes. Building on these results we created the *Pathway Platform* which includes a newer iteration of the Pathway App along with real time patient level data shared with the EMR integration in real-time and educational program both care team and patient facing.

We aim to implement a digitally enabled care pathway referred to as the *Pathway Platform* and assess its impact on measurement-based care and other evidence-based processes. The primary objective is to determine whether PHQ-9 utilization, a measurement- based practice, is greater after the Pathway Platform implemented.

3. STUDY DESIGN

We will use a pre- post- study design to assess the impact of implementing the Pathway Platform in the primary care setting. Clinic performance and select patient outcomes will be compared before and after implementation. Additional patient outcomes will be assessed after implementation among patients using the Pathway Platform (**Figure 1**).

This study will be performed within primary care clinics in Advocate's Health Care System. Advocate is the largest healthcare provider in the state of Illinois with 12 hospitals, 20 health centers, and 250+ care sites. It is one of the largest Accountable Care Organizations in the United States caring for over 2 million patients annually. General practitioners provide diagnoses, treatment, and clinical care for adults ages 18 and over with chronic diseases, which often includes MDD.

[figure not shown]
3.1 Performance among participating clinics post-implementation

The Pathway Platform will be implemented in up to 20 primary care sites within the Advocate Aurora Health system and enroll a total of 200 patients for six-month duration. The visit where the patient has been onboarded to the Pathway Platform will be the enrollment visit (Figure 1). During the post- implementation period, data on patient outcomes will be collected through the Pathway Platform. At the end of the study an electronic and manual chart review for patients using the Pathway Platform will be conducted among participating clinics and performance related to measurement-based care, shared decision making and collaborative care, where applicable, will be assessed over the post-implementation period.

3.2 Retrospective Assessment: pre-implementation performance at the clinic level (before Pathway Platform implementation)

To assess Advocate's primary care sites performance pre-implementation, an electronic and manual chart review will be conducted from the same Advocate primary care clinics participating in the implementation study. Patients with a clinic visit at least 6 months prior to implementation (index visit) of the Pathway Platform and meeting the inclusion criteria for enrollment in the study, will be included in this analysis (figure 1). Patient history will be evaluated for three months prior to index visit to confirm eligibility. The goal is to capture patients with a new start, dose adjustment or switch of an antidepressant medication 6 months prior to the implementation index date (three-month inclusion window for patient identification). Six months of patient history will be “retrospectively” collected for this baseline patient cohort to assess the primary outcome, defined as PHQ-9 utilization, and other secondary outcomes outlined in the protocol. This analysis will serve as the comparison control for the primary and secondary outcomes to compare performance at the same clinics pre and post-implementation of the Pathway Platform. Depending on the number of eligible patients identified per site (20 per site), group level matching for age and sex may be conducted. The primary endpoint will be the proportion of patients with at least 2 PHQ-9 scores.

Figure 1: Study schematic

* Primary and secondary outcomes will be evaluated at 6 months, data collected beyond 6 months will be used for exploratory analysis

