- e-Consenting virtually: If the patient is interested, the care team member will inform the research team, who will confirm eligibility and send a secure invitation to the patient (AAH patient portal or email with unique link and code). The invitation message includes a link to start the e-consenting process and that includes study contact information to allow patients to reach out to the study team with any questions during e-consenting or during the study. The link in the message will direct the patient to start the e-consenting process. The patient will not be able to download the app until they have completed the e-consenting process. Patient e-consent will be obtained in REDCap using a finger or stylus-directed signature on the mobile phone, with data including attestation of individual identity and time and date of signing. Upon completion, participants will be able to download a pdf copy of the signed e-consent form. The patient will then be invited to download the Pathway App via another secure message with a link including details for the patient to activate the mobile app and start entering data.

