5.2 Description of study evaluations

1. EMR data pulls and manual chart reviews: EMR data and manual chart review data will be collected from two cohorts of patients: (1) patients attending clinics after implementation (post- implementation cohort) and (2) patients attending clinics before implementation (pre-implementation). For the pre-implementation cohort, data will be collected over a six-month period. For the post-implementation cohort, data will be collected from the time of study implementation until the end of the study.
2. Pathway Platform data and analytics: Data on patient outcomes and Pathway Platform usage will be collected throughout the study starting at day 1 and ending on the final day of the patient's participation (i.e. 6 months, common study end date or patient withdrawl). Similarly, data on report usage by care team will be collected throughout the study.
3. Educational resource center analytics: The number of times material in the resource center is viewed will be recorded between day 1 and the end of the study.

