7. INTERVENTION DISCONTINUATION

Patients are not required to use the Pathway Platform and can choose to discontinue at any time. Adherence to use will be tracked and reported for analytical purposes.

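### Section 3.1 ties the post-implementation cohort to onboarding and app use, so patients who consent but never activate the app can drop out of the primary denominator

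*Combined protocol and SAP*

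**What the plan says.** The primary outcome (section 8.3.1) is at least 2 PHQ-9 scores in the EMR over the initial 6 months, compared as a proportion between the two cohorts.

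The post-implementation cohort is described in several ways:

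- **Section 3.1, time zero:** "The visit where the patient has been onboarded to the Pathway Platform will be the enrollment visit".
- **Section 3.1, chart review:** "an electronic and manual chart review for patients using the Pathway Platform will be conducted among participating clinics".
- **Synopsis, Sample Size and Population:** "We intend to enroll 200 patients who meet the eligibility criteria for this study and agree to download the Pathway Platform".
- **Synopsis, Design and Outcomes:** 200 patients enrolled in the Platform.
- **Section 5.2:** "patients attending clinics after implementation (post- implementation cohort".

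Section 4.3 puts activation after consent on both routes. In person, the link is sent once consent is given and the patient then activates the app. On the virtual route, e-consent is completed first: "The patient will then be invited to download the Pathway App via another secure message". Section 7 adds: "Patients are not required to use the Pathway Platform and can choose to discontinue at any time". It then says that adherence to use will be tracked for analysis.

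The pre-implementation cohort (sections 3.2 and 8.4) needs eligibility and at least one clinic visit in the period. No later engagement is required. Sections 8.3 and 8.4 name no analysis set and no rule for patients who consent but never activate, or who activate and stop.

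**The concern.** A patient can sign consent and never activate the app. Read literally, section 3.1 may give that patient no enrolment visit and no chart review, even though the EMR outcome is available. The pre cohort has no matching filter: someone who disengages after the index visit still counts, usually as a non-event.

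The filter sits close to the endpoint. The app prompts a PHQ-9 every two weeks (section 4.4.1) and the data go to the EMR (section 4.4.2), so an active user can reach 2 scores within weeks. A denominator restricted to users would favour the Platform. It would also answer a narrower question than section 1.1, which compares patients attending clinics after implementation with those attending before.

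This is separate from the difference between people who consent and people who merely attend. It concerns removal after consent, which the plan can avoid entirely.

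**Working it through.** **1. Which wording keeps whom.**

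| Description of post cohort | Consented, never activated | Onboarded, later stopped |
|---|---|---|
| Patients using the Platform (3.1) | out, read literally | unclear |
| Onboarded at the enrolment visit (3.1) | depends on what onboarded means | in |
| Enrolled in the Platform (synopsis) | unclear | in |
| Agree to download (synopsis) | in | in |
| Attending clinics after implementation (5.2) | in | in |

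The first group's status changes with the sentence chosen. The second group is in under every wording but one.

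**2. The plan's own figure.** Section 8.2 assumes 75% before and 90% after, 80% power, two-sided alpha 0.05 and a Pearson chi-square test. With pooled variance under the null:

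n = [1.960·√(2·0.825·0.175) + 0.8416·√(0.75·0.25 + 0.90·0.10)]² / 0.15² = 99.5, rounded up to 100 per group, as stated.

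Power is 80.2% at 100 per group and 97.9% at the planned 200. The sample-size figure is sound. It contains no allowance for non-activation.

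**3. No true effect, non-activators left out (illustration).** The documents give neither the share a who never activate nor their rate q of reaching 2 scores. Assume a = 10–30% and q = 50–70%, with 75% among all consenters (the plan's pre rate). The proportion among those kept is

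(0.75 − a·q) / (1 − a).

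| a | q = 70% | q = 60% | q = 50% |
|---|---|---|---|
| 10% | 75.6% | 76.7% | 77.8% |
| 20% | 76.3% | 78.8% | 81.3% |
| 30% | 77.1% | 81.4% | 85.7% |

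The spurious gain runs from 0.6 points (0.68/0.90 = 75.6%) to 10.7 points (0.60/0.70 = 85.7%). With 200 pre patients and 200·(1 − a) post patients, the chance of a significant result at q = 60% (50%) is 6.6% (9.7%) for a = 10%, 13% (29%) for 20%, and 28% (68%) for 30%, against a nominal 5%. If q were 75%, this bias would be zero.

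**4. A real effect in users, everyone consented analysed.** Take 90% in users and the pre rate of 75% in non-users. The all-consented proportion is 0.90·(1 − a) + 0.75·a.

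| a | Post proportion | N per group for 80% power | Power at 200 per group |
|---|---|---|---|
| 10% | 88.5% | 128 | 94.1% |
| 20% | 87.0% | 167 | 86.7% |
| 30% | 85.5% | 225 | 75.3% |

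So a users-only denominator would report 1.5, 3.0 or 4.5 points more than the all-consented one, even when non-activators behave exactly like pre patients.

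**The case against.** The fair opposing reading is that the word using in section 3.1 is shorthand for the post cohort as opposed to the pre cohort. The same section speaks of enrolling 200 patients for six months, and no section sets a minimum level of use, excludes non-users or replaces anyone. Table 1 puts consent and onboarding together on Day 0, ahead of the Day 1 Platform baseline, so onboarding may not mean activation. Agreeing to download would also keep a consented non-activator in. This stands as far as it goes: a reading that retains these patients is available. It does not settle the matter, because onboarded is undefined and the only section that names whose charts are reviewed for post-implementation performance names users.

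Two stronger inferences are tempting, and the documents do not support them.

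- **That patients who stop the app are dropped.** Study Duration (numbered 3.3) collects EMR process measures after 6 months of enrolment, not of use. Section 5.2 ends Platform data when participation ends but runs post-cohort EMR collection to study end. Section 8.3.3 compares the primary outcome by app utilization, which needs low users in the data. These point to retention. Moreover, a patient who answers two prompts and then stops may already meet the endpoint, so dropping such patients need not raise the post proportion.
- **That the primary difference is inflated.** The text permits the exclusion but does not require it, and the size in step 3 rests wholly on assumed rates. Setting q below 75% produces a gain by construction, and 10.7 points is the extreme corner of both ranges.

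**Conclusion.** The plan leaves the primary post-implementation denominator open on one group: patients who consent but never activate. Taken literally, section 3.1 allows them to be left out, with no equivalent in the pre cohort. The likely direction favours the Platform because app use feeds the endpoint directly. The size cannot be computed from the documents. The 0.6–10.7 point range is an illustration that depends on assumed non-activation of 10–30% and an assumed 50–70% rate in those patients. Onboarded patients who later stop appear to be kept, and the plan should say so. The stated 100 per group is correct and is not in question.

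**What to change.** In sections 3.1 and 8.3.1, define the primary post-implementation cohort as every eligible patient who signed consent. Start the 6-month EMR window at the visit that led to consent. Carry out the EMR pull and chart review for all of them whatever their activation or later use, and do not replace non-activators or stoppers.

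Then:

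- align the synopsis (both cohort descriptions), section 3.1 and section 5.2 with that definition, and define onboarding;
- keep the users-only result as a secondary analysis;
- report the numbers consented, activated and stopped;
- record stopping the app separately from withdrawing permission for chart review.

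The cost is wording changes, a few more chart reviews in patients who have already consented, and a somewhat less favourable primary proportion. Under step 4, power at 200 per group stays above 80% with 20% non-users but falls to 75.3% with 30%, so the expected activation share should be stated beside the sample size.
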